7.7 EXTENT OF EXPOSURE

Exposure will be analyzed on the treated set. Extent of exposure will be summarized using descriptive statistics for days of exposure as well as number (%) of patients whose total exposure falls in the categories specified in Section 5.4.2.

7.8 SAFETY ANALYSIS

All safety analyses will be performed on the treated set. Analyses are specified in section 7.3.4 of the CTP.

7.8.1 Adverse events

Unless otherwise specified, the analyses of adverse events will be descriptive in nature. All analyses of AEs will be based on the number of subjects with AEs and NOT on the number of AEs.

For analysis multiple AE occurrence data on the CRF will be collapsed into an AE provided that all of the following applies:

- All AE attributes are identical (LLT, intensity, action taken, therapy required, seriousness, reason for seriousness, relationship, outcome, AE of special interest)
- The occurrences were time-overlapping or time-adjacent (time-adjacency of 2 occurrences is given if the second occurrence started on the same day or on the day after the end of the first occurrence).

For further details on summarization of AE data, please refer to (3, 4).

The analysis of adverse events will be based on the concept of treatment emergent adverse events. That means that all adverse events occurring between first drug intake till last drug intake + residual effect period will be assigned to the randomised treatment. All adverse events occurring before first drug intake will be assigned to 'screening' and all adverse events occurring after the residual effect period will be assigned to 'post-treatment' (for listings only). For details on the treatment definition, see Section 6.1.

According to ICH E3 (5), AEs classified as 'other significant' need to be reported and will include those non-serious and non-significant adverse events with:

(i) 'action taken = discontinuation' or 'action taken = reduced', or

Proprietary confidential information © 2021 Boehringer Ingelheim International GmbH or one or more of its affiliated companies

(ii) marked haematological and other lab abnormalities or lead to significant concomitant therapy as identified by the Clinical Monitor/Investigator at a Medical Quality Review Meeting.

An overall summary of adverse events will be presented.

The frequency of subjects with adverse events will be summarized by treatment, primary system organ class and preferred term. Separate tables will be provided for subjects with other significant adverse events according to ICH E3 (5), for subjects with adverse events of special interest (detailed in section 5.2.6.1 of the revised CTP) and for subjects with serious adverse events.

The system organ classes will be sorted alphabetically, preferred terms will be sorted by frequency (within system organ class).

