### Information required

For each AE, the investigator should provide the information requested on the appropriate eCRF pages and the BI SAE form, if applicable. The investigator should determine the causal relationship to the trial medication.

The following should also be recorded as an (S)AE in the CRF and BI SAE form (if applicable):

- Worsening of the underlying disease or of other pre-existing conditions
- Changes in vital signs, ECG, physical examination and laboratory test results, if they are judged clinically relevant by the investigator.

If such abnormalities already pre-exist prior to trial inclusion they will be considered as baseline conditions and should be collected in the eCRF only. All (S)AEs, including those persisting after individual patient's end of trial must be followed up until they have resolved, have been assessed as "chronic" or "stable", or no further information can be obtained.

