### **7.3.4 Safety analyses**

Adverse events will be coded using the Medical Dictionary for Regulatory Activities (MedDRA). Standard BI summary tables and listings will be produced. All adverse events with an onset between start of treatment and end of the residual effect period (REP), a period of 7 days after the last dose of trial medication, will be assigned to the on-treatment period (see above) for evaluation.

All treated patients will be included in the safety analysis. In general, safety analyses will be descriptive in nature and will be based on BI standards. No hypothesis testing is planned.

Statistical analysis and reporting of adverse events will concentrate on treatment-emergent adverse events, i.e. all adverse events occurring between start of treatment and end of the

residual effect period. Adverse events that start before first drug intake and deteriorate under treatment will also be considered as ‘treatment-emergent’.

Frequency, severity, and causal relationship of adverse events will be tabulated by system organ class and preferred term after coding according to the current version of MedDRA at the database lock.

Laboratory data will be analysed both quantitatively as well as qualitatively. The latter will be done via comparison of laboratory data to their reference ranges. Values outside the reference range as well as values defined as clinically relevant will be summarised. Treatment groups will be compared descriptively with regard to distribution parameters as well as with regard to frequency and percentage of patients with abnormal values or clinically relevant abnormal values.

Vital signs, physical examinations, or other safety-relevant data observed at screening, baseline, during the course of the trial and at the end-of-trial evaluation will be assessed with regard to possible changes compared to findings before start of treatment.

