3. INTRODUCTION

As per ICH E9, the purpose of this document is to provide a more technical and detailed elaboration of the principal features of the analysis described in the protocol, and to include detailed procedures for executing the statistical analysis of the primary and secondary variables and other data.

This TSAP assumes familiarity with the Clinical Trial Protocol (CTP), including Protocol Amendments. In particular, the TSAP is based on the planned analysis specification as written in CTP Section 7 "Statistical Methods and Determination of Sample Size". Therefore, TSAP readers may consult the CTP for more background information on the study, e.g., on study objectives, study design and population, treatments, definition of measurements and variables, planning of sample size, randomization.

SAS® Version 9.4 or higher will be used for all analyses.

Proprietary confidential information © 2021 Boehringer Ingelheim International GmbH or one or more of its affiliated companies

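### SAP 7.8.1 omits the protocol's rule that adverse events starting before first intake and worsening under treatment are treatment-emergent, so such worsening can be left out of the tables

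*SAP*

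**What the plan says.** Protocol Section 7.3.4 gives two routes to treatment-emergent status. The first is occurrence between the start of treatment and the end of the residual effect period, which is 7 days after the last dose. The second concerns events that were already present: "Adverse events that start before first drug intake and deteriorate under treatment will also be considered as" treatment-emergent.

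SAP Section 7.8.1 also bases its analysis on treatment-emergent events, but explains the term by the window alone: "all adverse events occurring between first drug intake till last drug intake + residual effect period will be assigned to the randomised treatment". For earlier events it says "All adverse events occurring before first drug intake will be assigned to" screening, and it marks that category, like the post-treatment one, as for listings only. Worsening of an event that began before the first dose is not mentioned.

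The SAP elsewhere ties itself to the protocol. Section 7.8 states "Analyses are specified in section 7.3.4 of the CTP", and Section 3 states that "the TSAP is based on the planned analysis specification as written in CTP Section 7". Section 4, which records departures from the protocol's analysis, contains nothing on the definition of treatment-emergent events.

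**The concern.** A programmer who implements SAP Section 7.8.1 as written would take the onset date, compare it with the first intake and send every earlier event to the screening listing. A programmer who implements protocol Section 7.3.4 would also check whether the event worsened on treatment and, if so, put it in the tables. The same patient can be handled in two ways, and both programmers could cite a governing document.

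There is a real period in which such events can arise. Adverse events are collected from consent onwards, and the Flow Chart places Visit 1 between 28 and 7 days before randomisation. The safety analysis is descriptive and counts subjects with events, so the classification rule decides what the tables show. Worsening of a symptom that was already present is one form that an adverse drug effect can take in chronically ill patients, and the protocol chose to count it.

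**Working it through.** No arithmetic applies. The plan states no figure on this point, and the documents give neither the number of events with pre-dose onset nor the share that worsen. The check is a comparison of the two rules, case by case.

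| Case | Protocol 7.3.4 | SAP 7.8.1 as written |
|---|---|---|
| A. Onset between first intake and end of residual effect period | Treatment-emergent | Treatment-emergent |
| B. Onset before first intake, no worsening | Not treatment-emergent | Screening, listing only |
| C. Onset before first intake, worsening entered as a new record with on-treatment onset | Treatment-emergent | Treatment-emergent through the new record |
| D. Onset before first intake, worsening on treatment, one record with the original onset date | Treatment-emergent | Screening, listing only |

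The rules agree in A, B and C and disagree in D. Three questions decide whether D matters.

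1. **Does the SAP's verb cover D?** The SAP speaks of events occurring, not starting, in a window, so one could argue that worsening on drug occurs on drug. The protocol uses the same verb for its base window and still adds a separate sentence for events that deteriorate. In the sponsor's own usage, then, the base wording does not include D.

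2. **Does data capture turn every D into a C?** Under Information required (protocol Section 5.2.6.2), the protocol asks for this to be recorded as an adverse event: "Worsening of the underlying disease or of other pre-existing conditions". That covers conditions known at entry. It does not say that an adverse event already open since screening receives a second record with a new onset date. The protocol's deterioration sentence would have little purpose if it always did.

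3. **Does the collapsing rule protect the worsening?** SAP Section 7.8.1 merges overlapping or adjacent occurrences only when "All AE attributes are identical (LLT, intensity, action taken, therapy required, seriousness, reason for seriousness" and the remaining listed attributes match. Two records of different intensity therefore stay separate. But the rule only keeps apart records that already exist. It does not create a second record, and it does not separate two records when the worsening leaves every listed attribute unchanged.

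Case D is therefore possible under the documents, and it is the only case in which the two rules give different tables.

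**The case against.** The strongest reply is that the protocol rule is already in force. SAP Section 7.8, the parent of 7.8.1, adopts protocol Section 7.3.4 by reference, and silence in Section 4 most naturally means that no change was intended. This stands as evidence of intent. It does not settle implementation, because the specific definition in 7.8.1 says something different from the section that its parent adopts.

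The second reply is that much on-treatment worsening reaches the tables anyway. Worsening of pre-existing conditions is recorded as an event in its own right. Reports of suicidal ideation of type 4 or 5 and of suicidal behaviour must each be reported as separate serious events (protocol Section 5.2.5.1). Clinically relevant changes in vital signs are recorded as events, and vital signs also have their own summary. Records that differ in intensity are not merged. All of this stands and narrows the problem to case D.

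The third reply is that SAP Section 7.8.1 refers further summarisation detail to sponsor standards (references 3 and 4), which may deal with worsening. They may, but they are not part of the documents and cannot be relied on either way.

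A reader might infer more than the text allows: that all on-drug worsening of screening events disappears from the tables, or that the safety comparison is thereby biased towards no difference. The documents support neither. Loss requires a single record classified by its original onset date, and the documents do not say how the CRF records a change in intensity. The direction of any bias would depend on whether such worsening differs between arms, which is unknown. A reader might also multiply the planned 387 patients by assumed rates. The documents give no such rates, and SAP Section 4 reports that recruitment stopped early with a reduced sample. In addition, the tables count subjects, so a patient with another on-treatment event would still appear in the overall count.

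**Conclusion.** The conflict between SAP Section 7.8.1 and protocol Section 7.3.4 is real and is not declared as a change. Its effect is conditional. If a worsening screening event is kept as one record and assigned by its original onset date, its on-treatment worsening can be left out of the treatment-emergent tables. No loss of events has been shown, and neither the number affected nor the direction of any bias can be derived from the documents. The conclusion rests on reading 7.8.1 literally and on the absence of any statement about how a change in intensity is captured. If every worsening is entered as a new record with on-treatment onset and survives the collapsing rule, the tables would be the same under both rules. The change is still worth making, because the SAP states a rule that contradicts the protocol on a safety definition and the correction costs almost nothing.

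**What to change.** Amend SAP Section 7.8.1 to carry over the protocol rule, for example: adverse events with onset before first intake that worsen between first intake and the end of the residual effect period are treatment-emergent (CTP Section 7.3.4); only those that do not worsen in that window are assigned to screening. The sentence should name the window, because the protocol's rule refers only to deterioration under treatment.

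In the same place, state how worsening is identified: by a new record with on-treatment onset, or by a flag in the adverse event dataset.

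The cost is one SAP sentence and one dataset flag. No new data collection is proposed, and the change restores what the protocol already specifies.

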7.8.2 Laboratory data

The analyses of laboratory data will be descriptive in nature and will be based on BI standards (6). Planned analyses are detailed in section 7.3.4 of the revised CTP.

Baseline for safety laboratory parameters will be the last available measurement before the start of randomized treatment.

Laboratory measurements taken up to 7 days after the last administration of randomized treatment will be considered as on-treatment.

Only patients with at least one available on-treatment value will be included in the analysis of an individual laboratory parameter. All individual data will be presented in listings.

If there are multiple safety laboratory values at one visit, the worst of these will be assigned to that visit date measurement.

7.8.3 Vital signs

Only descriptive statistics are planned for this section of the report. The latest measurement will be analyzed if multiple assessments are completed during the same visit window. See section 7.3.4 of the revised CTP.

7.8.4 ECG

Any clinically significant new findings in the ECG measurement after the first ECG will be considered as AE and analyzed as planned in Section 7.8.1.

7.8.5 Others

Taper/withdrawal (T/W) period

The 7-day, post 28 week treatment T/W period will not be analyzed as part of the primary analyses. Planned analyses on the T/W period will be descriptive only

Vital signs, suicidality and adverse events will be closely monitored during this period T/W. Only data obtained during the T/W period will be included in the analyses, and only of those patients randomized to the active treatment arms will be included in comparisons, which include all tapering comparing to all withdrawal as well as comparisons between the individual doses.

IDEA for CON.

TSAP for BI Trial No: 1289-0049 Page 32 of 35

[figure not shown]
Proprietary confidential information © 2021 Boehringer Ingelheim International GmbH or one or more of its affiliated companies

8. **REFERENCES**

1.	CPMP/ICH/363/96: "Statistical Principles for Clinical Trials", ICH Guideline Topic E9, Note For Guidance on Statistical Principles for Clinical Trials, current version.
2.	001-MCS 36-472: "Standards and processes for analyses performed within Clinical Pharmacokinetics/Pharmacodynamics", current version; IDEA for CON.
3.	001-MCG-156_RD-01: "Handling of missing and incomplete AE dates", current version; IDEA for CON.
4.	001-MCG-156: "Handling and summarization of adverse event data for clinical trial reports and integrated summaries", current version; IDEA for CON.
5.	CPMP/ICH/137/95: "Structure and Content of Clinical Study Reports", ICH Guideline Topic E3; Note For Guidance on Structure and Content of Clinical Study Reports, current version
6.	001-MCG-157: "Handling, Display and Analysis of Laboratory Data", current version;

TSAP for BI Trial No: 1289-0049 Page 33 of 35

Proprietary confidential information © 2021 Boehringer Ingelheim International GmbH or one or more of its affiliated companies

Proprietary confidential information © 2021 Boehringer Ingelheim International GmbH or one or more of its affiliated companies

9.3 ADDITIONAL ANALYSIS FOR IMPACT OF THE COVID-19 PANDEMIC ON THE TRIAL

9.3.1 Start and end of COVID-19 disruption

The trial specific start date of COVID-19 disruption is defined as the date of earliest COVID-19 related event, including COVID-19 related protocol deviation, discontinuation of a subject's treatment with study drug or trial participation due to COVID-19, or onset of a SARS-CoV-2 related AE. In this trial, start date of COVID-19 disruption is 13-Mar-2020 as it is the date of first occurrence of COVID-19 related protocol deviation.

As of now, end of the impact is not foreseeable so it will not be defined for this trial.

9.3.2 Additional analysis

Additional outputs will be included in CTR to assess the impact of COVID-19 on the trial, and it will include analyses of the following:

- Disposition
- Premature discontinuation
- COVID-19 related iPD
- Study medication exposure
- Compliance with study medication
- Adverse events

TSAP for BI Trial No: 1289-0049 Page 35 of 35

Proprietary confidential information © 2021 Boehringer Ingelheim International GmbH or one or more of its affiliated companies

10. HISTORY TABLE

History table Table 10: 1

Version	Date (DD-MMM-YY)	Author	Sections changed	Brief description of change
Initial	01-DEC-17		Initial	This is the initial TSAP with necessary information for trial conduct
V2	27-NOV-18		Initial sections were only modified to change "iPV" to "iPD"; All other sections were populated	This is the final TSAP
V3	26-Feb-2021			Updated version to reflect sponsor's decision to stop trial earlier, implement fast-track approach to expedite decision making and for preparation of the planned phase III trials. and add more analysis to assess COVID-19 impact.
V4	17-Mar-2021			Updated a typo in the date of signature
